### **Tumor Tissue**

**Processing of specimen:** The study team will process and embed the fresh tissue obtained from the pathology department to an FFPE block for downstream studies. Alternatively, the biologic correlate study team will request 20 x 5 µm unstained FFPE slides from the diagnostic tissue after surgical pathology clinical review is complete. The specimens will be labeled with the research study number, "surgical resection," and section number, if applicable. The label will be stripped of all patient identifiers, such as the medical record number or dates.

Research Tissue samples and PDXs within the context of this protocol will be maintained under the supervision of [name] located at:  
University of Wisconsin  
[name]

[name]  
[name]

### **Circulating Tumor Cells/Biomarkers**

Processing of specimen: The samples will be picked up by a member of the biologic correlative study team and transported to [name] lab. Upon arrival at the lab, PHI patient identifiers will be stripped from the sample and relabeled. The samples will be labeled with the subject's study ID number and coded time point (1- baseline, 2- pre-surgical resection, 3- one month post surgery, 4- three months post definitive-treatment, 5- twelve months post definitive treatment). Processing and storage of the circulating tumor cell samples within the context of this protocol will occur under the supervision of [name] lab located at:

Pharmaceutical Sciences Division  
University of Wisconsin School of Pharmacy  
[name]  
[name]  
[name]

### **Determination of putative biomarkers of CTX sensitivity**

The biologic correlate study team will formalin fix and paraffin embed (FFPE) approximately one third of the research biopsy tissue to be used to assess putative biomarkers of CTX sensitivity (e.g. total and phosphorylated AXL, EGFR and HER3 expression using immunohistochemistry assays). The FFPE research and surgical specimens will be used to establish the change in Ki67 ( $\Delta$ Ki67).

Correlations between the change in Ki67 index ( $\Delta$ Ki67) and AXL expression and HER3 expression in the research biopsy will be performed. Further correlation between other biomarkers and AXL expression will be performed.

### **Determination of circulating tumor cells**

We hypothesize that changes in circulating tumor cells detected using the described head and neck cancer optimized capture approach (section 2) will correlate with response as determined by change in Ki67. Circulating tumor cells will be quantified at each time point. In addition, we plan to utilize captured circulating tumor cells to establish the first reported circulating tumor cell-derived head and neck cancer patient derived xenografts and to compare these PDXs to those established using standard techniques.

#### **8.2.4 Specimen Shipment**

Not applicable.

## 9 ASSESSMENT OF SAFETY

### 9.1 Specification of Safety Parameters

Adverse event data collection and reporting, which are required as part of every clinical trial, are done to ensure the safety of patients enrolled in the studies as well as those who will enroll in future studies using similar agents. Adverse events are reported in a routine manner at scheduled times during a trial. Additionally, certain adverse events must be reported in an expedited manner to allow for optimal monitoring of patient safety and care. The first step is to identify the event using the Common Terminology Criteria for Adverse Events (CTCAE). The CTCAE document provides descriptive terminology for adverse event reporting. A grading (severity) scale is provided for each adverse event term.

Adverse events, Serious adverse events and unanticipated problems will be recorded on the study eCRF's and reported per section 9.4. Certain toxicities are known and can be expected.

#### Cetuximab:

*Common:* Change in nails, rash, itching, dry skin, acne, dehydration, weight loss, loss of appetite, sores in mouth which may cause difficulty swallowing, constipation, diarrhea, vomiting, nausea, difficulty sleeping, headache, tiredness, pain, fever, infection, especially when white blood cell count is low, cough, shortness of breath, hypomagnesemia, hypokalemia and hypocalcemia

*Occasional:* Allergic reaction which may cause rash, low blood pressure, wheezing, shortness of breath, swelling of the face or throat, confusion, depression, worry, fainting, severe blood infection, blood clot which may cause swelling, pain, shortness of breath

*Rare:* Scarring of the lungs, kidney damage which may require dialysis, cardiac arrest

#### Additional risks from study procedures

##### *Biopsy*

Possible risks from a tissue biopsy include bleeding and infection. There can also be some degree of pain associated with the biopsy.

##### *Blood draw*

Possible risks include: pain, bleeding and/or bruising, feeling faint, infection with redness, irritation, and, more rarely, a blood clot in the vein at the site where the blood is drawn.

---

In addition to physical risks there is also the risk of “breach of confidentiality”. If this occurs, it will be reported as an unanticipated problem.

### **9.1.1 *Unanticipated Problems***

The Office for Human Research Protections (OHRP) considers unanticipated problems involving risks to subjects or others to include, in general, any incident, experience, or outcome that meets **all** of the following criteria:

- unexpected in terms of nature, severity, or frequency given (a) the research procedures that are described in the protocol-related documents, such as the IRB-approved research protocol and informed consent document; and (b) the characteristics of the subject population being studied;
- related or possibly related to participation in the research (“possibly related” means there is a reasonable possibility that the incident, experience, or outcome may have been caused by the procedures involved in the research); and
- suggests that the research places subjects or others at a greater risk of harm (including physical, psychological, economic, or social harm) than was previously known or recognized.

### **9.1.2 *Adverse Events***

An adverse event is any untoward or unfavorable medical occurrence in a human subject, including any abnormal sign (for example, abnormal physical exam or laboratory finding), symptom, or disease, temporally associated with the subject’s participation in the research, whether or not considered related to the subject’s participation in the research.

### **9.1.3 *Serious Adverse Events***

A serious adverse event (SAE) is one that meets one or more of the following criteria:

- Results in death
- Is life-threatening (places the subject at immediate risk of death from the event as it occurred)

- Results in inpatient hospitalization or prolongation of existing hospitalization
- Results in a persistent or significant disability or incapacity
- Results in a congenital anomaly or birth defect
- An important medical event that may not result in death, be life threatening, or require hospitalization may be considered an SAE when, based upon appropriate medical judgment, the event may jeopardize the subject and may require medical or surgical intervention to prevent one of the outcomes listed in this definition.

## **9.2 Time Period and Frequency for Event Assessment and Follow-Up**

Unanticipated problems will be recorded in the data collection system throughout the duration of the study.

All AE's will be recorded from the time of informed consent until 28 days past last dose of study drug or day of surgery, whichever is first. SAE's will be recorded from the time of informed consent through 28 days past last dose of study drug or 28 days post-surgery, whichever is later. Serious adverse events that occur more than 28 days after surgery and have an attribution of possibly, probably, or definitely related to cetuximab (or other research procedures such as biopsy or blood draws) require reporting per table 1.

At each study visit, the investigator will inquire about the occurrence of AE/SAEs since the last visit. Events will be followed for outcome information until resolution or stabilization.

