### **3.2.2 Secondary Endpoint**

*The rate of hospital re-admissions for wound care or surgical complications attributed to cetuximab (such as fistula or deep cellulitis) within 28 days after surgery*

Although the use of cetuximab pre-operatively has been studied in a pre-operative trial, this clinical trial will expand upon this information to further evaluate any other complications during surgery due to pre-operative cetuximab. We will also plan a descriptive analysis of all AEs and SAEs associated with pre-operative cetuximab.

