### Cetuximab Administration in the Pre-operative Setting

Cetuximab is an FDA approved chemotherapy agent for the treatment of (a) locally or regionally advanced squamous cell carcinoma of the head and neck in combination with radiation therapy, (b) recurrent locoregional disease or metastatic squamous cell carcinoma of the head and neck in combination with platinum-based therapy with 5-FU, and (c) recurrent or metastatic squamous cell carcinoma of the head and neck progressing after platinum-based therapy. Treatment with cetuximab prior to surgical resection is considered the investigational portion of this study, as neoadjuvant cetuximab is not considered standard of care. However, treatment with cetuximab as a monotherapy may offer a benefit to patients as cetuximab is a known and approved chemotherapy agent for the treatment of head and neck cancer. In patients with recurrent and/or metastatic HNSCC with progression on platinum-based chemotherapy, those patients who were treated with cetuximab monotherapy had overall response rates from 10-13% and disease control rates from 46-56%. Although surgical resection will offer definitive treatment for local HNSCC, use of neoadjuvant cetuximab may offer disease response such as shrinkage of the tumor that may offer improved surgical resection.

Cetuximab will be given twice via IV infusions at pre-specified doses within a 14-day period between the time of their biopsy confirming their cancer and their scheduled surgery. Given that the standard of care time interval between diagnosis/consult and curative surgical resection is approximately 4-6 weeks at the University of Wisconsin, treatment with pre-operative cetuximab is not anticipated to delay curative surgical resection. No dose reductions of cetuximab are allowed although the rate of infusion of the drug can be reduced at the discretion of the investigator as per the standard of care infusion rate modifications noted in the FDA prescribing information of cetuximab.

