### Surgical Resection

The surgical resection is considered standard of care therapy for this study population. Patients will undergo definitive standard of care surgery within 4 weeks of the first protocol dose of cetuximab.

Specimens from the tumor resection will be transferred to pathology in culture media or saline per standard operating procedures. The biologic correlate study team will wait for the pathology team to access the specimen in the gross room and then will be given a portion of tissue that will not be required for diagnosis (i.e., remnant). The study team will then process and embed that fresh tissue to an FFPE block for downstream studies. Alternatively, the biologic correlate study team will request 20 x 5  $\mu$ m unstained FFPE slides from the diagnostic tissue after surgical pathology clinical review is complete.

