#### *Dermatologic Toxicity*

Dermatologic toxicities, including acneiform rash, skin drying and fissuring, paronychial inflammation, infectious sequelae (for example, *S. aureus* sepsis, abscess formation, cellulitis, blepharitis, conjunctivitis, keratitis/ulcerative keratitis with decreased visual acuity, cheilitis), and hypertrichosis occurred in patients receiving cetuximab therapy. Acneiform rash occurred in 76–88% of 1373 patients receiving cetuximab. Severe acneiform rash occurred in 1–17% of patients. Acneiform rash usually developed within the first two weeks of therapy and resolved in a majority of the patients after cessation of treatment, although in nearly half, the event continued beyond 28 days.

- Study subjects will be monitored for dermatologic toxicities and infectious sequelae.
- Subjects will be instructed to limit sun exposure during cetuximab treatment
- Severe (NCI CTC Grade 3 or 4) acneiform rash will result in discontinuation of cetuximab therapy.

- Intolerable grade 2 rash, despite maximum supportive care, will result in discontinuation.
- NCI CTC Grade 1 or 2 rash is to be treated with one or more of the following medications at the treating physician's discretion, based upon supportive care evidence. Potential medications that can be used for the treatment of cetuximab-related rash may include, but are not limited to, the following:
  - Hydrocortisone 1 to 2.5% lotion
  - Doxycycline 100 mg bid
  - Clindamycin 1% lotion

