## **9.4 *Reporting Procedures***

### **Procedures for Recording Adverse Events**

- AEs will be recorded from time of informed consent until 28 days post discontinuation of study drug or day of surgery, whichever is first.
- AEs will be recorded regardless of whether or not they are considered related to the study intervention.
- AEs will be recorded in the subject's medical record and in the research study records.

- All AEs considered related to study drug(s) or procedure will be followed until resolution to ≤ Grade 1 or baseline, deemed clinically insignificant, and/or until a new anti-cancer treatment starts, whichever occurs first.
- At the 3 month and 12 month follow up visits, any AEs deemed by treating physician or study PI to be probably related to the research blood draw procedure will be recorded at time of visit and followed until resolution to ≤ Grade 1 or baseline, deemed clinically insignificant.

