### FOOTNOTES

1. Pre-study tests to be done within 21 days of dose 1 cetuximab therapy.

2. Time between doses: 7 days (+/-3 days)
3. Informed consent to be obtained within 28 days of starting treatment.
4. If screening/baseline procedures are within 7 days prior to cetuximab dose 1, they don't need to be repeated on day of dose 1.
5. Serum chemistry should include: sodium, potassium, chloride, bicarbonate, BUN, creatinine, glucose, AST, ALT, alkaline phosphatase, total bilirubin, calcium, magnesium, protein, albumin.
6. A negative serum/urine pregnancy test is required within 7 days prior to cetuximab dose 1.
7. For subjects with unresolved treatment-related toxicity, follow as medically appropriate until resolution or stabilization.
8. Pre-surgical blood draw for circulating tumor cells in serum should be done within 1 day prior to surgery.
9. Prior to dose 2, required labs: magnesium, calcium and potassium
10. Definitive therapy is defined as surgery alone, surgery + XRT or Surgery + chemoXRT
11. Within 7 days prior to surgery, but as close as possible to surgery.
12. May include any of the SOC imaging such as PET/CT, PET/MRI, CT or MRI
13. Blood Pressure only

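### For patients dosed and operated on schedule, non-serious adverse event recording ends on the day of surgery, and the one-month complication check has no stated route into the visit list or the analysis

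*Combined protocol and SAP*

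**What the plan says.** Section 9.2 collects AEs from consent "until 28 days past last dose of study drug or day of surgery, whichever is first". Section 9.4 (Procedures for Recording Adverse Events) repeats the rule: "AEs will be recorded from time of informed consent until 28 days post discontinuation of study drug or day of surgery, whichever is first". For serious adverse events (SAEs), Section 9.2 uses the opposite connective: "through 28 days past last dose of study drug or 28 days post-surgery, whichever is later".

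The timing comes from elsewhere. Section 4 (Surgical Resection) states: "Patients will undergo definitive standard of care surgery within 4 weeks of the first protocol dose of cetuximab". Section 7.2 and Appendix A, footnote 2, put dose 2 seven days after dose 1, give or take three days. Section 4 (Cetuximab Administration in the Pre-operative Setting) sets an outer limit: "Cetuximab will be given twice via IV infusions at pre-specified doses within a 14-day period".

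The secondary objective is the safety of pre-operative cetuximab. Its formal endpoint in Section 3.2.2 is readmission attributed to cetuximab within 28 days after surgery. The same section adds: "We will also plan a descriptive analysis of all AEs and SAEs associated with pre-operative cetuximab".

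Section 4 (Post-Surgical Assessment) also calls for readmission, wound healing and infection to be assessed one month after surgery, give or take two weeks, with a five-level attribution to cetuximab.

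**The concern.** The safety question in this trial concerns what two doses of cetuximab before an operation do to the patient around and after that operation. The AE rule closes general recording on the day of surgery, while Section 3.2.2 promises a description of all AEs associated with the drug. A wound problem or infection managed without admission is not counted by the readmission endpoint. Unless it is judged serious, it is also outside the AE window. If the Section 4 check is its only route, that check needs a place in the visit schedule and the analysis. Otherwise the safety description will be thin for the post-operative period that the secondary objective is about.

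**Working it through.** The plan gives no figure to reproduce. The check is day arithmetic, followed by a comparison of the sections.

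**Inputs** (dose 1 = day 0)
- L, day of last dose: 4 to 10 (Section 7.2; Appendix A, footnote 2), or 14 at the outer limit of the 14-day period in Section 4.
- S, day of surgery: no later than 28 (Section 4, Surgical Resection).
- End of AE recording = min(L + 28, S) (Sections 9.2 and 9.4).
- End of SAE recording = max(L + 28, S + 28) (Section 9.2).

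**Which limit applies when both doses are given and surgery is on time?**

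| Dose 2 on day L | L + 28 | Latest planned surgery | Surgery comes first by at least |
|---|---|---|---|
| 4 | 32 | 28 | 4 days |
| 7 | 35 | 28 | 7 days |
| 10 | 38 | 28 | 10 days |
| 14 (outer limit) | 42 | 28 | 14 days |

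No permitted combination has L + 28 ≤ S, so recording ends on day S. Days after surgery covered: S − S = 0 for AEs; (S + 28) − S = 28 for SAEs. With surgery on day 28, AE recording ends on day 28 and SAE recording on day 56.

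**When can the 28-day limit matter?**
- One dose only: L + 28 = 0 + 28 = 28, a tie with the latest planned surgery.
- Late surgery: the limit comes first only if S > L + 28, that is, after day 32 to 38. Recording then stops before the operation.
- No surgery: recording runs to L + 28.

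None of these adds post-operative days.

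**Where would a new post-operative event be captured?**
- *Readmission:* meets the hospitalization criterion in Section 9.1.3, falls in the SAE window, and is analysed in Section 12.4.
- *Related AE that began before surgery:* recorded, then followed under Section 9.4 to grade 1 or baseline, clinical insignificance, or new anti-cancer treatment.
- *New non-serious wound problem or infection:* outside the AE window, inside the Section 4 check. The list for SOC Follow Up Visit 1 in Section 7.2 names only SAE evaluation, the AE row in Appendix A stops at Study Visit 5, and Section 12.4 analyses only readmissions.
- *New non-serious cetuximab-related event of another kind, such as a non-infectious skin event:* outside the AE window and not named in the Section 4 check. Section 9.4 makes a late exception for blood-draw AEs at 3 and 12 months, but none for cetuximab-related AEs at one month.

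Two smaller mismatches belong with these. Section 9.2 has the investigator ask about AEs and SAEs at each study visit, although it has already closed AE recording. The attribution labels in Section 4 also differ from those in Section 9.3.1.

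**The case against.** The strongest reply is that the rule is deliberate. Section 9.2 sets the earlier date for AEs directly beside the later date for SAEs. In a single-arm trial, routine post-operative events are heavily confounded by the operation, so SAEs plus a targeted complication check is a defensible design. The 28-day clause also has a use, as a backstop for patients whose surgery is late or does not happen. Section 12.2 keeps any biopsied patient in the safety set. All of this stands, and it argues for restricting what is added.

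Several stronger readings are tempting but not supported:
- A reader might infer that outpatient wound events are lost. The Section 4 check has no seriousness or admission threshold, so it covers them. A complication that prolongs the surgical stay, or is judged an important medical event, is an SAE under Section 9.1.3.
- A reader might infer that the secondary endpoint is compromised. It counts readmissions, which the SAE window covers.
- A reader might cite Section 6.2.1 on rash ("in nearly half, the event continued beyond 28 days") as evidence of late skin events being missed. That statement concerns persistence. The same sentence says rash usually starts within the first two weeks, and rash that starts before surgery is recorded and followed.
- A reader might count days lost from a 28-day post-dose window. The plan promises no such window for AEs, only the earlier of two dates, and does not give a usual day of surgery.

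Silence in Appendix A is weak evidence by itself, because the table also omits the SAE evaluation and medication review that Section 7.2 requires at the one-month visit. However, the visit list in Section 7.2 and the analysis in Section 12.4 do not mention the complication check either.

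**Conclusion.** The point holds in a limited form. For every patient who receives both doses and has surgery on schedule, general AE recording ends on the day of surgery: 0 post-operative days, against at least 28 for SAEs. New non-serious post-operative events are therefore outside the AE data that would feed the description in Section 3.2.2. The Section 4 check asks for part of this information, but no visit list, schedule row or analysis takes it up. Other new non-serious cetuximab-related events after surgery have no stated route into the study data.

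This rests on surgery by day 28 and dose 2 on day 4 to 10; extending dose 2 to day 14 does not change it. How many events are involved cannot be estimated, because the documents give no rate of non-serious post-operative events. The effect is confined to the supplementary safety description. This is an inconsistency worth repairing because the repair is cheap.

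**What to change.** Reconcile Section 4 (Post-Surgical Assessment), the SOC Follow Up Visit 1 list in Section 7.2, Sections 9.2 and 9.4, Section 12.4 and Appendix A:

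- Keep the present AE rule for general events, and add that wound, infection and fistula events, and any non-serious event at least possibly related to cetuximab, are recorded through 28 days after surgery, matching the SAE window.
- List the complication check at the one-month visit and in Appendix A, with a case report form and one set of attribution labels.
- In Section 12.4, report these events descriptively (counts and proportions by type, grade and attribution) beside the readmission rate.

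The visit may fall two weeks early. Taking a month as 30 days, that is day 30 − 14 = 16 after surgery, which leaves 28 − 16 = 12 days uncovered. A record review at day 28 would close that gap when the visit is early.

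The cost is some extra data entry; the visit and the attribution step already exist. The downside is some surgical background events, which the restriction by category and attribution limits. Only data capture and reporting change; clinical management does not.
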